### **6.2.2 Adverse Events Definition and Reporting**

There are no anticipated adverse events with our proposed intervention.

## **6.3 Study Procedures**

### **6.3.1 Study Schedule**

See section 6.1.4 for intervention schedule. Data on control group CRC screening rates will be collected from clinic's electronic medical records system (EMR) after the intervention period is over and prior to beginning data analysis.

### **6.3.2 Informed Consent**

We are seeking a full waiver of informed consent and HIPAA authorization for the purpose of determining eligibility and group assignment. We are seeking a waiver of written documentation of consent for the intervention group and a full waiver of informed consent for the usual care group for the duration of the study. This research is minimal risk and involves the promotion of a recommended, standard-of-care, preventative health screening for which patients are due or overdue to undergo. By foregoing informed consent prior to mailing the FIT kit, we will avoid selection bias of enrolling individuals whom are particularly interested in receiving CRC screening or research, thus improving our study's external validity and more accurately measuring the potential efficacy of our intervention on the population at large. In short, the traditional consenting process would negatively impact the reliability of study outcomes.

Additionally, providing information about the study prior to offering the proactive CRC screening to intervention patients may interfere with decision-making and the clinical care

process. The possible perception that CRC screening is research may negatively impact an individual's behavior, attitudes towards such screening, or their willingness to undergo any type of screening in general, due to fear or other stigma associated with research.

Providing information about the study to the standard-care (control) group could also influence decision-making regarding CRC screening and interfere with the clinical care process for these patients.

The waiver of documentation of consent for the intervention group will include the subset of intervention patients who complete the qualitative interview. Information about the interview is included in the Study Information Sheet provided to all intervention patients in the initial FIT kit mailing. The study coordinators will verbally consent those patients who opt-in for the interview, using a study-specific NYU telephone consent script.

### **6.3.3 Screening**

Screening for participant eligibility will be performed through the research team accessing patient charts through the Flatbush FHC's EMR (Epic) and applying the inclusion and exclusion criteria previously stated.

### **6.3.4 Recruitment, Enrollment and Retention**

Patients will be identified for inclusion in the study via accessing the Flatbush FHC EMR (Epic) and applying the inclusion and exclusion criteria previously mentioned. We will work with DataCore to obtain an initial list of eligible patients once, at the beginning of the study. The PI and study coordinators will be the only research staff with access to the list. The list will contain the following information about the eligible patients: MRN, full name, date of birth (or age), address, phone number(s), email addresses, biological sex, race, ethnicity, height/weight (or BMI), smoking status, and primary care physician's name. Data for the patients that will not be included in the study will be deleted from the electronic list provided by DataCore at the end of the study. No information will be retained about these patients.

After the mailed intervention process is complete, data regarding colorectal cancer screening will be obtained for the control group patients. This will include whether colonoscopy, FIT, or other screening tests for colorectal cancer were completed during the study period. Approved waiver of consent and HIPAA authorization for this patient group will allow this information to be collected directly from Epic by the study team.

The primary care physicians at Flatbush FHC have been notified that their intervention group patients will be contacted directly by the study team regarding this mailed CRC screening effort. All letters from the FHC (initial and final) will contain their electronic signature. These patients will receive the Study Information Sheet as part of the initial FIT kit mailing (first contact). If they decide to opt out, only de-identified data will be retained in REDCap for audits, summaries, and reporting purposes.

Subjects in the usual care group will not be approached or notified of their enrollment in the study.

### **6.3.5 Study Visits**

There are no study visits associated with this protocol. Colonoscopy is also considered standard-of-care CRC screening and is not a study procedure. The only potential visits, possibly facilitated by the study team, would be for patients opting to be screened via colonoscopy or navigating to diagnostic colonoscopy following a positive FIT test result. These non-study visits are detailed below.

In person pre-colonoscopy screening visit (if applicable and if required, days 7-180): Patient will receive instruction from a certified R.N. or M.D. regarding colonoscopy preparation instructions, if not already provided by the colonoscopy provider. Estimated length of visit: 10-20 minutes

Colonoscopy procedure visit (if applicable, days 7-180): Patient will have colonoscopy performed by certified gastroenterologist at the Brooklyn Family Health Center facility or another facility at which they have access for this procedure.

### **6.3.6 End of Study and Follow Up**

Following the completion of the intervention period of the study, we will administer interviews to a subset of patients randomized to the proactive screening arm regarding barriers to completion of colorectal screening, perceived effectiveness of the proactive outreach screening program, and any unexpected adverse effects that the patient may have experienced. Patients receiving the intervention can participate in an interview regardless of whether or not they completed CRC screening.

The interviews will be conducted by a member of the NYULH research staff trained in qualitative interviewing techniques and will occur either over the telephone or through HIPAA-compliant WebEx sessions. The interviews will be audio recorded and transcribed, with any identifiers to be removed from the transcription records. The interviews will take about 15 minutes to complete. Recording is required for participation.

### **6.3.7 Removal of Subjects**

Given the nature of our proposed study and waiver of informed consent, participants in the usual care group will be unaware of their participation in this research study and thus will not actively withdraw from the study. Participants randomized to the intervention group may opt out of the screening program or refuse screening at any time. Instructions for how to opt out will be provided in the study information sheet included in the initial mailing. Once 50 of the eligible individuals are randomized to proactive screening and 50 to usual care, those selected to proactive screening will be mailed the FIT kit packet and this number will serve as our denominator for the remainder of the study.

At any point, if a patient initially randomized into the intervention group is found to no longer receive their medical care at Flatbush FHC or their address is deemed undeliverable by the United States Postal Service, they may be replaced at the discretion of the PI to ensure 50 eligible patients receive the proactive intervention. If this occurs, control group participants would be replaced based on the same criteria. Replacements would be determined by the study biostatistician.

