#### **5.3.3 Exclusion Criteria**

- Age younger than 45 years old or greater than 75 years old
- Up-to-date with colorectal cancer screening (FIT within 1 year or colonoscopy within 10 years)
- History of colorectal cancer, inflammatory bowel disease or colorectal polyps
- No address or phone number on file
- FIT test ordered within 6 months

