#### **6.1.4 Intervention Administration**

Please note: all days listed beyond day 0 have a +5 day tolerance window.

Day 0: Patients randomized to the proactive outreach group will be mailed letters explaining CRC screening options and a FIT kit with detailed instructions for collection and submission.

Day 10-14: In the proactive outreach group, if a FIT kit has not been submitted by this time point, the patient will receive a call or voice message from our research team to ensure FIT kit was received and reminding the patient to complete and return it or request a new kit, if necessary.

Day 28: If the FIT kit has not been submitted, the patient will receive a final letter reminding the patient to complete and return the FIT kit.

Day 56: For patients who have still not submitted a FIT kit or requested screening via colonoscopy, there will be a final note in the chart alerting the patient's primary care physician to complete further action regarding CRC screening as indicated.

Days 7-180: Patients with a positive FIT test result will receive assistance with navigation to scheduling a follow-up colonoscopy. If patients indicated that they prefer colonoscopy to FIT testing, they will also receive assistance with navigation to scheduling a colonoscopy. Assistance to scheduling a colonoscopy will include an initial phone call performed by our research coordinator or appropriate clinic staff to triage whether a colonoscopy can be scheduled over the phone or requires an in-person pre-colonoscopy visit. In addition, study staff will ensure bowel prep will either be mailed to the patient with instructions or made available to pick-up in clinic, depending on patient preference. Finally, bowel preparation instructions and appointment

reminders will be performed via phone call, text or mail 5-7 days prior to scheduled colonoscopy.

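### Replacing randomised outreach patients after allocation contradicts intent-to-screen, and its returned-mail trigger cannot arise in usual care as described, so the comparison could favour outreach

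*Combined protocol and SAP*

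**What the plan says.** Section 6.3.7 first fixes the analysis set: once 50 patients are randomised to each arm and the outreach packets are mailed, "this number will serve as our denominator for the remainder of the study". The next paragraph opens it again. With no time limit, an outreach patient found to have left the clinic, or whose address the postal service finds undeliverable, may be exchanged: "they may be replaced at the discretion of the PI to ensure 50 eligible patients receive the proactive intervention".

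Two safeguards follow: "control group participants would be replaced based on the same criteria", and "Replacements would be determined by the study biostatistician".

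Other sections bear on whether these can work:

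- Section 6.3.4: "Subjects in the usual care group will not be approached or notified of their enrollment in the study".
- Section 6.3.1: "Data on control group CRC screening rates will be collected from" the clinic's electronic record, once the intervention period has ended.
- Section 5.3.3 has the exclusion "No address or phone number on file", which concerns whether contact details exist, not whether mail arrives.
- Section 6.1.4 defines the start of follow-up by the mailing: "Day 0: Patients randomized to the proactive outreach group will be mailed letters".
- Sections 6.4.1 and 6.4.3 call for intent-to-screen analysis of all participants. Section 5.1 rests allocation concealment on randomising everyone at once. The Synopsis describes the study as non-blinded.

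**The concern.** Intent-to-screen protects the comparison because the groups analysed are the groups randomised. A rule that exchanges people after allocation, so that a target number receive the intervention, gives that up. If replaced patients are dropped, the analysis no longer covers everyone randomised. If they are kept, the outreach denominator exceeds 50. The plan does not say which is meant, although a denominator fixed at 50 suggests they leave. It also sets no cut-off for replacement and does not say when Day 0 and the 6-month window begin for a late replacement.

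The more serious matter is asymmetry. Returned mail can be seen only where mail is sent. If patients with bad addresses also complete screening less often, removing them from outreach while their counterparts remain in usual care raises the outreach rate relative to control without any effect of the programme.

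The estimate would also describe outreach to people with deliverable addresses, not outreach to the clinic's list. Undeliverable mail is a real limit of a mailed programme, and the clinic needs to know how common it is when judging feasibility.

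**Working it through.** **1. The two triggers, arm by arm**

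| Trigger | Outreach | Usual care |
|---|---|---|
| Left the clinic | Electronic record, and also calls and mailings | Electronic record only; a check made when outcomes are extracted could coincide with sight of the outcome |
| Address undeliverable | Returned mail | No mailing and no address check described |

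The first trigger can be applied to both arms. The second cannot, as the plan is written.

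**2. Inputs for sizing the bias**

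From the documents: 50 per arm (Section 5.3.1) and an independent two-sample t-test (Section 6.4.3.1). The sample size rests on feasibility (Section 6.4.2), so there is no power calculation to reproduce.

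Assumed, because the documents do not give them: two-sided alpha 0.05; no true effect; completion among reachable patients p_r = 20–40%; unreachable share u = 4%, 10% or 20% (2, 5 or 10 of 50); completion among the unreachable p_u equal to zero or half of p_r.

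**3. Formula**

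With replacement in outreach only, and replaced patients dropped:

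- outreach rate = p_r
- control rate = (1 − u) × p_r + u × p_u
- spurious difference = u × (p_r − p_u)

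Example: u = 10%, p_r = 30%, p_u = 0 gives 0.10 × 0.30 = 3 points.

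**4. Results**

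Rejection rates come from exact enumeration of two binomials of 50, using the pooled t-test on 98 degrees of freedom. Ranges run over p_r = 20–40%.

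| Scenario | u | Spurious difference (points) | All rejections | Rejections favouring outreach |
|---|---|---|---|---|
| No replacement, or equal replacement in both arms | – | 0 | 4.9–5.2% | 2.4–2.6% |
| p_u = half of p_r | 4% | 0.4–0.8 | 4.9–5.3% | 2.7–3.1% |
| | 10% | 1–2 | 5.1–5.7% | 3.2–4.1% |
| | 20% | 2–4 | 5.6–7.1% | 4.3–6.2% |
| p_u = 0 (worst case) | 4% | 0.8–1.6 | 5.0–5.5% | 3.1–3.7% |
| | 10% | 2–4 | 5.6–7.1% | 4.3–6.2% |
| | 20% | 4–8 | 7.8–13.2% | 7.2–12.9% |

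If half of the unreachable controls were also found and replaced, with p_u = 0, all rejections would be 5.1–5.7% at u = 10% and 5.6–7.1% at u = 20%.

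**5. Would perfect symmetry cure it?**

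Take true rates among reachable patients of 20% (usual care) and 40% (outreach), u = 10%, p_u = 0.

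- Everyone as randomised: 0.9 × (40 − 20) = 18 points.
- Replacement in both arms: 40 − 20 = 20 points.
- Replacement in outreach only: 40 − 0.9 × 20 = 22 points.

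Equal replacement keeps the test valid when there is no effect, but it estimates the effect in reachable patients, not in everyone randomised.

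**The case against.** The strongest reply is that the plan does provide a counterpart: controls are to be replaced on the same criteria, and what is missing is only the method. The initial patient list holds addresses for everyone eligible (Section 6.3.4), so a control's address could be checked without contacting the patient. Discretion is limited to two triggers, neither defined by the screening outcome, and the biostatistician, not the PI, determines who comes in. The fixed number can also be read as a count of 50, which replacement preserves.

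On size, the worst case is hard to support for addresses. Usual-care screening is offered when a patient is seen (Section 2.1), so a bad postal address need not prevent it. If controls with bad addresses complete at the same rate as others, the bias under no effect is exactly zero. At three-quarters of the reachable rate, all rejections are 4.9–5.3% at u = 10% and 5.1–5.7% at u = 20%. Nothing in the documents supports a 20% unreachable share.

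Much of this stands as a limit on size, and it is why the bias is stated conditionally. It does not remove the contradiction. An address check in controls is possible but not planned, and reading the number as a count still exchanges people after allocation. Estimating the effect in reachable patients is a legitimate aim, but the plan declares intent-to-screen instead.

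**Conclusion.** The concern holds and should be fixed. That the replacement rule conflicts with intent-to-screen analysis and single-time-point randomisation follows from the text and needs no assumption. So does the absence of any described means of finding an undeliverable address in usual care.

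Bias toward outreach requires three things: replaced patients leave the analysis, replacement is more frequent in outreach, and the replaced patients would have completed screening less often. The plan makes the first two likely; the third is plausible but not documented. Under the stated assumptions the distortion is negligible to minor at 4% unreachable. At 10% it is 1–4 points, with outreach-favouring false positives of 3.2–6.2% against about 2.5%. It becomes material only if unreachable patients are common and rarely screened. Each replaced patient is 1/50, or 2 points, of an arm's denominator.

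**What to change.** Amend Section 6.3.7 so that no replacement enters the primary analysis. Analyse every patient originally randomised in the assigned arm, by the 6-month outcome in the electronic record, including those later found undeliverable or departed.

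Before randomisation, check clinic status and address for all candidates on the single eligibility list, so that the check is identical for both arms. Report the number undeliverable as an implementation result. Any analysis with replacements, or restricted to patients successfully mailed, should be a labelled sensitivity analysis, with replacements counted by arm and reason and Day 0 defined for each.

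The cost is a wording amendment and one check of one list. Slightly fewer than 50 patients may receive a kit, and the observed outreach rate may be a little lower. No power target is lost, since the sample size rests on feasibility. Screening done elsewhere by departed patients may be missed in the record, but this should affect both arms alike.

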## **6.4 Statistical Method**

### **6.4.1 Statistical Design**

The intent-to-screen principle will be utilized to analyze all participants for completion of the primary outcome variable of completion of colonoscopy or FIT testing screen at 6 months. The intent-to-screen principle will also be utilized to analyze all participants for completion of the secondary outcome variable of completion of colonoscopy in patients with a positive FIT test at 6 months. Analysis will be conducted utilizing an independent two sample t-test.

### **6.4.2 Sample Size Considerations**

Sample size selection (n = 100) for this pilot study was based on feasibility.

### **6.4.3 Planned Analyses**

The intent-to-screen principle will be utilized to analyze all participants for completion of the primary outcome variable of completion of colonoscopy or FIT testing screen at 6 months. The intent-to-screen principle will also be utilized to analyze all participants for completion of the secondary outcome variable of completion of colonoscopy in patients with a positive FIT test at 6 months. Analysis will be conducted utilizing an independent two sample t-test.

#### **6.4.3.1 Primary Analyses**

Analysis will be conducted utilizing an independent two sample t-test.

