## 2 - Background

### 2.1 Background

Colorectal Cancer (CRC) is the third most common cancer in men and women and the second leading cause of cancer related death. Screening for CRC reduces CRC incidence and mortality, and is recommended for average risk men and women between the ages of 45 and 75 by the US Preventive Services Task Force guidelines; which were updated recently to include 45-49 year olds, an additional 20 million individuals in the US. In New York State, CRC screening rates are over 70% but only 48-52% in Brooklyn family health centers (FHC) that provide free and subsidized health services to underrepresented minorities. Currently, invitations to screen are offered only when a patient is seen by his or her provider. Consequently, many eligible individuals, particularly 45-55 year olds who do not regularly access healthcare are underscreened.

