## 3 - Rationale/Significance

### 3.1 Problem Statement

CRC screening rates are 72% in New York State but 48-55% in the federally qualified health center where we anticipate performing the study. Hence, there is an unmet need to organize and implement CRC screening using multilevel interventions to improve screening rates.

The current model for CRC screening is far from optimal and poses many barriers at the patient, provider and systems level. At the patient level: the current model requires an in-person or telehealth visit, which poses barriers through difficulty accessing transportation, time commitments and financial barriers. Furthermore, men and women aged 45-55 (on the younger end of the screening spectrum) may not have a primary care provider or seek routine medical care. Many individuals may not know they are eligible for CRC screening or the benefits of CRC screening. At the provider level, barriers include lack of up to date information and a lack of time to address CRC screening in a short clinic visit with many pressing urgent medical needs. The alternative method of screening we are proposing, an organized program of proactive invitation, has two main components: 1) *identification* of screen eligible individuals using health records from the clinic; and 2) a *proactive invitation* program, with (a) mailed invitation, (b) a package of materials so patients can complete a fecal immunochemical test (FIT) from their homes (i.e., FIT kit), and (c) instructions on how to schedule colonoscopy if they prefer this to completing the FIT. From a public health perspective, an outreach screening program is more likely to reach all individuals eligible for screening.

Multiple trials have reported higher screening rates with proactive invitation through outreach efforts and programmatic approaches, compared to usual care. Kaiser Permanente Northern and Southern California implemented proactive outreach screening in 2008, based primarily on annual FIT. Their reported rates of CRC screening are one of the highest in the country, at 81%. In their recent publication, they reported that 323,349 health plan members were reached through the program. Completion rates for screening improved from 48% to 86% over 4 rounds of implementing the outreach screening process. The program detected 80% of patients diagnosed with stage I colon cancer within 1 year of screening.

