#### 5.2.1 Primary Outcome Variables

The primary outcome variable is completion of initial fecal immunochemical test (FIT) or colonoscopy at 6 months.

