#### **6.1.2 Method of Assignment/Randomization**

The study biostatistician will randomize 50 eligible patients to proactive outreach and 50 eligible patients to usual care, stratified by age and biological sex. Proactive outreach patients will be blind to the presence of an alternative group assignment and "usual care" patients will be unaware of group assignment altogether.

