#### **6.4.3.3 Analysis of Subject Characteristics**

We will summarize baseline and demographic characteristics utilizing standard descriptive summaries (means and standard deviations for continuous variables such as age and percentages for categorical variables gender).

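### Randomisation is stratified by age and sex, but the yes/no primary outcome is compared with an unstratified t-test, which loses some precision if age or sex predicts completion

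*Combined protocol and SAP*

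**What the plan says.** On allocation, section 6.1.2 states: "The study biostatistician will randomize 50 eligible patients to proactive outreach and 50 eligible patients to usual care, stratified by age and biological sex". It gives no age categories, so the number of strata is not known.

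On the outcome, section 5.2.1 states: "The primary outcome variable is completion of initial fecal immunochemical test (FIT) or colonoscopy at 6 months". Each patient therefore contributes a yes or a no.

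On the analysis, section 6.4.3.1 states: "Analysis will be conducted utilizing an independent two sample t-test". Sections 6.4.1 and 6.4.3 name the same test. None of the three mentions strata, covariates, an effect measure or a confidence interval.

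Age and sex come back only in section 6.4.3.3, for description: "We will summarize baseline and demographic characteristics utilizing standard descriptive summaries". The secondary outcome on factors associated with non-adherence (section 5.2.2) has no model, and would not adjust the primary comparison in any case.

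On size, section 6.4.2 states: "Sample size selection (n = 100) for this pilot study was based on feasibility".

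**The concern.** Stratified randomisation makes the arms alike in age and sex. If those factors predict completion, the true sampling error of the difference between arms becomes smaller. An unstratified t-test does not recognise this: its standard error still contains the variation between strata. The interval is then wider than it needs to be, and the test rejects less often than its nominal level.

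What is at stake is precision. The study is a pilot with 50 patients per arm, its size cannot be raised to compensate, and section 7.11 says its data may inform funding proposals. The design does the work of stratifying, and the analysis then discards whatever benefit there is.

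The fact that a t-test is applied to binary data is not the problem. At 50 per arm with no stratum effect, its type I error in simulation was 4.8% to 5.1%.

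**Working it through.** **No figure to reproduce.** The plan states no power, significance level, expected rates or target effect. What follows uses the 50 per arm from the plan. All completion rates, the number of strata, the effect sizes and the two-sided 5% level are assumptions. The site figure in section 3.1, "but 48-55% in the federally qualified health center where we anticipate performing the study", is overall screening coverage, not 6-month completion among patients already due or overdue, so it does not supply a usual-care rate.

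**Mechanism.** Let stratum s have completion rate p_s and share w_s, with overall rate p̄ = Σ w_s p_s. With no treatment effect and 50 per arm:

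- standard error used by the t-test ≈ √[2 p̄(1 − p̄)/50]
- true standard error with balanced strata ≈ √[2 Σ w_s p_s(1 − p_s)/50]

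Take rates of 10/15/25/30% in strata of 13/12/13/12 per arm:

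- p̄ = (1.30 + 1.80 + 3.25 + 3.60)/50 = 0.199, so p̄(1 − p̄) = 0.1594
- Σ w_s p_s(1 − p_s) = (1.170 + 1.530 + 2.4375 + 2.520)/50 = 0.1532
- standard errors: √(2 × 0.1594/50) = 0.0798 against √(2 × 0.1532/50) = 0.0783
- the t-test's standard error is about 2% too large

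**Power, type I error and interval width.** 200,000 simulated trials per scenario, strata of 13/12/13/12 per arm, common log odds ratio 1.2 (odds ratio e^1.2 ≈ 3.3), and 0 for type I error. The pooled t-test is compared with the Cochran-Mantel-Haenszel (CMH) test without continuity correction.

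| Usual-care rates by stratum | Power, t-test | Power, CMH | Type I error, t-test | Mean 95% interval width, t vs stratified |
|---|---|---|---|---|
| 20% in all (not prognostic) | 78.3% | 78.2% | 4.8% | 0.358 vs 0.358 |
| 15/15/25/25% (mild) | 76.5% | 77.1% | 4.7% | 0.358 vs 0.354 |
| 10/15/25/30% (moderate) | 73.8% | 75.6% | 4.5% | 0.357 vs 0.347 |
| 5/15/25/35% (very strong) | 68.3% | 72.5% | 4.1% | 0.356 vs 0.334 |
| 5/10/30/45% (very strong) | 61.4% | 69.8% | 3.4% | 0.364 vs 0.326 |

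- CMH type I error was 4.9% to 5.0% throughout.
- Power gained: −0.1, 0.6, 1.8, 4.2 and 8.4 points.
- Interval narrower by 0%, 1%, 3%, 6% and 10% (for example 1 − 0.347/0.357 = 2.8%).
- The last two rows need odds ratios between extreme strata of (0.35/0.65)/(0.05/0.95) ≈ 10 and (0.45/0.55)/(0.05/0.95) ≈ 15.
- Six strata: 78.0% (t-test) vs 77.9% (CMH) if not prognostic, and 74.7% vs 75.9% for rates spread over 10–30%.
- Average rate 50%, strata 40/45/55/60%: 79.6% vs 80.0%.

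**Second method.** A linear model with stratum terms was compared with the t-test in 20,000 trials per scenario, four strata, true difference 25 points.

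- Usual care 20%: 77.0% (t-test) vs 77.1% (adjusted) with no stratum effect; 77.5% vs 78.5% when stratum rates vary by ±10 points; 78.3% vs 82.1% at ±20 points.
- Usual care 30%: 73.6% vs 73.6%, 74.0% vs 74.1%, and 75.0% vs 77.1%.
- At 20% and ±20 points, the t-test's mean standard error was 0.0902 while the true standard deviation of the estimate was 0.0855, a ratio of 1.055. With no treatment effect, its type I error was 3.4%, against 5.0% for the adjusted model. This is an extreme case: the lowest stratum then has 0% completion under usual care.

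**Choice of interval.** In the four-stratum scenarios, coverage of the true Mantel-Haenszel risk difference was:

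- t-interval: 95.0% rising to 97.3% as the strata become more prognostic
- plain stratified Wald interval: 93.5% to 93.7% (about 93% with six strata)
- stratified interval with n − 1 variances and a t quantile: 94.8% to 95.0%

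**The case against.** The strongest reply is that little is lost and nothing in the documents shows a loss. The estimate is essentially unchanged, the test errs on the safe side, and a feasibility-sized pilot promises no power that the t-test would fail to deliver. Every rate above is assumed, and the 4 to 8 point losses need odds ratios of 10 to 15 between extreme strata. Section 2.1 says only that many eligible people, "particularly 45-55 year olds who do not regularly access healthcare are underscreened", which says nothing about 6-month completion among patients already due or overdue, and nothing about sex. All of this stands. It limits the point to an inexpensive improvement whose size is unknown and probably small.

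A second reply is that the simulations impose balance within strata. Section 6.1.2 describes no blocking, and section 6.3.7 allows replacements without saying that they are matched on stratum. With weaker balance the t-test is less conservative than shown. That is right, but it does not remove the case for stratifying. Without within-stratum balance the stratified analysis still gains when the strata are moderately or strongly prognostic, and costs at most about 1 point of power otherwise.

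A third reply is that several adjusted methods are valid, and that a CMH p-value and a separately built interval can occasionally disagree. This is also true: a linear model with stratum terms gives estimate, test and interval from one fit. The choice among valid methods is open; using the strata is what matters.

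**Conclusion.** The point holds. The plan randomises within age and sex strata and then ignores them in the primary comparison. There is no bias and no excess of false positives. The cost is a standard error and interval that are too wide to the extent that age or sex predicts completion.

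Under the assumed rates, the loss is nil to about 2 points of power, with an interval up to 3% wider than needed, for strata that range from not prognostic to moderately prognostic. It reaches 4 to 8 points only for very strong strata. The actual loss cannot be fixed from the documents. The change is still worth making: with balanced strata it costs about 0.1 point of power if they turn out not to matter, and N is not open to increase.

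**What to change.** In sections 6.4.1, 6.4.3 and 6.4.3.1, replace the t-test for the primary outcome with:

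- **Estimate:** the Mantel-Haenszel risk difference (proactive outreach minus usual care) across the age-by-sex strata used in the randomisation.
- **Test:** the CMH test without continuity correction, two-sided 5%.
- **Interval:** a 95% confidence interval from the stratum-weighted variance, with n − 1 within-stratum variances and a t quantile on N minus twice the number of strata degrees of freedom (100 − 8 = 92 with four strata).
- **Sparse strata:** merge any stratum with fewer than two patients in an arm into the adjacent age category of the same sex.
- **Reporting:** numbers and proportions completing by arm, with the unadjusted comparison as supportive.

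In section 6.1.2, state the age categories used for stratification.

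The cost is a few sentences and no new data. Age (or date of birth) and biological sex are already on the eligibility list in section 6.3.4. The de-identified file sent to the biostatistician (sections 7.3 and 7.9) must carry the stratum label, which is easiest to arrange in advance.
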